6.5.9 Bladder Mapping

During the cystoscopic exams, a standardized video capture protocol for bladder mapping will be followed in order to assess any changes in the number, size, and severity of lesions during the study as a result of treatment.

6.5.10 Insertion and Removal of IP

For instructions on insertion and removal of IP, please see the Study Manual.

6.5.11 Post-use Assessment

Immediately after removal of the IP, the investigator will take 2 photographs of the IP (wireform side up and wireform side down), and will perform a visual inspection of the IP to confirm that it was removed from the patient in its entirety and none of the IP components (nitinol wire, silicone) are missing. The investigator will document any observations of visible damage or changed appearance of IP (eg, wireform protrusion, torn silicone, change in color, etc) in the eCRF, and notify Allergan or designee within 48 hours so that a product investigation can be initiated if appropriate. If the IP is not removed from the patient in its entirety, the investigator should conduct appropriate testing to confirm that no IP components are left indwelling in the patient, such as a pelvic examination, abdominal x-ray, abdominal ultrasound, and/or cystoscopic exam.

Each IP removed from the bladder of a study patient will be retained and sent to Allergan for a post-use assessment. Detailed instructions for the storage and shipment of the IP post-removal are provided in the Study Manual.

6.5.12 Bladder Pain NRS

A pain assessment tool will be utilized in the study to capture the daily average pain and the daily worst pain scores on an electronic hand held device. Patients will be asked to rate their daily pain on a pain NRS consisting of an 11-point integer scale ranging from 0 for "no pain" to 10 for "worst pain imaginable". The pain assessment tool will be provided to patients at the Screening visit and patients will be instructed on how to correctly complete the bladder pain assessment by the site staff. If the patient has a confirmed or suspected UTI, pain data should not be collected until the signs and symptoms of the UTI have resolved.

The pain assessment will continue every day up to and including the day prior to the Exit Visit. Patients should complete the pain assessment questions at approximately the same time each day on the pain assessment tool (preferably at the end of each day, prior to 12:00 midnight, with instruction that it reflects the last 24-hour period).

Baseline and Follow-up Visit Pain Assessment

The baseline pain assessment will be calculated based on at least 5 consecutive days of data collected in the 7 days immediately prior to the Randomization/Day 0 visit to determine eligibility and obtain baseline values. Pain assessment data collection should be completed for at least 14 days immediately prior to Randomization/Day 0 in order to acclimate the patient to the process of assessing their pain on a daily basis. The primary timepoint for the

daily average pain score is at 4 weeks following Treatment 1, 2nd IP removal. The patient's Pain NRS for this timepoint will be the average of the 7-day "average pain in your bladder over the last 24 hours".

If the patient's study visit is rescheduled, the site must ensure that adequate time has been provided for the patient to record at least 5 consecutive pain assessment days during the 7 days immediately prior to the rescheduled visit.

6.5.13 Bladder Diary

[figure not shown]
A paper bladder diary will be utilized in the study to capture micturition parameters. Prior to receiving the diary, patients will be instructed and trained on the use of the diary, the data to be collected and instructed on how to correctly complete the bladder diary by the site staff.

[figure not shown]
Patients should enter data into the bladder diary following each void (day and night) for 3 consecutive days immediately prior to the designated clinic visit (see Table 1).

The 3-day bladder diary will capture the number of day-time voids and the number of nighttime voids (where night time is defined as the time the patient goes to bed until the time the patient gets out of bed the next morning) over a period of 3 days. Patient will also indicate all urinary urgency episodes defined as time they experienced a sudden and urgent need to urinate whether it was associated with a recorded void or not. The bladder diary will also capture patient-reported pre-void and post-void bladder pain.

6.5.14 Pain Catastrophizing Scale

The PCS is a 13-item self-administered scale which assesses the psychological impact of pain that will be evaluated at the Screening visit for study eligibility. Items are rated on a scale from 0 to 4 and the PCS has 3 different categories: Rumination, Magnification, and Helplessness. It is hypothesized that pain catastrophizing is related to various levels of pain, physical disability, and psychological disability in clinical and nonclinical populations.

6.5.18 Concomitant Medications and Concurrent Procedures

Patients will be instructed to capture all pain medication (stable dose and rescue medications) taken for IC pain during the study on the electronic diary which will capture what medication was taken and when (date and time). Site staff will review the pain medication electronic

diary and capture missing or incomplete pain medication information as required. Site staff will also query patients regarding use of any other medications while participating in the study.

Concomitant medication information, including name of medication, dose, route, date will be collected at each study clinic and phone visit starting at the time of Screening and ending at the patient Exit Visit (either at completion of follow-up to Treatment 1 or Treatment 2, as applicable).

All concomitant medications and concurrent procedures must be recorded in the eCRF with all specific details associated with each use of the medication/procedure.

6.5.19 Adverse Events

Details regarding the definitions, documentation, and reporting of adverse events/serious adverse events are in Section 9.

6.5.20 IP Events

An IP event includes any observation of the IP not performing as intended. Examples of IP Events are:

- voiding of the IP
- damage to the IP during insertion or removal procedures
- damage to the IP that is not related to insertion or removal procedures

An IP Event could occur any time between when the IP is removed from the packaging through the insertion/removal procedures and the return of the IP.

Each IP Event will be assessed by the investigator to determine if it is associated with an adverse event, and any adverse events identified will be managed according to details in Section 9.

All IP Events, in the opinion of the investigator, should be reported to Allergan or designated representative.

6.6 Other Study Supplies

The following will be provided by Allergan:

6.7 Summary of Methods of Data Collection

Pain assessment and pain medication use will be recorded by the patient on an electronic diary. Voiding frequency and urgency, and pre- and post-void pain scores will be reported by patients in a paper bladder diary.

All clinical study data will be entered into an electronic data

capture (EDC) system via eCRFs. Source documents will be used and stored at the sites, and may include a patient's medical records, hospital charts, clinical charts, patient chart, copy of the EDC file, as well as the results of diagnostic tests (if performed).

7. Statistical Procedures

All statistical analyses will be detailed in the study statistical analysis plan (SAP), which will be finalized prior to database lock. This document will provide a more technical and detailed description of the proposed data analysis methods and procedures. Two analyses are planned for this study, including the primary analysis and the final analysis. The primary analysis will be conducted at the time when the last patient completes the primary timepoint that is Week 4 following Treatment 1 2nd IP removal. The final analysis will be conducted when all patients complete or exit the study.

7.1 Analysis Populations

The modified intent-to-treat (mITT) analysis population: The mITT population will include all patients who were randomized and received at least 1 IP insertion in Treatment 1. The efficacy data will be analyzed as randomized using the mITT population.

Safety analysis population: The safety population will include all patients enrolled in this study and received at least one IP. The safety data will be analyzed as treated using the safety population.

Pharmacokinetic evaluable population: The pharmacokinetic population will include all patients enrolled in this study and who have at least one plasma or urine pharmacokinetic concentration measurement post-IP insertion and for whom the IP is successfully removed.

Per-protocol (PP) analysis population: The PP population will include all patients who retain the 2 IP inserted in Treatment 1 for the 28 days of the treatment period and complete the 4 Week Follow-up Visit post removal of the 2^{nd} IP of Treatment 1 without any significant protocol deviations. Protocol deviations will be determined prior to database lock.

7.2 Collection and Derivation of Primary, Secondary, and Other Efficacy Assessments

Average daily bladder pain NRS: The pain NRS will be used to assess bladder pain over the previous 24-hour period. The pain NRS consists of an 11-point integer scale ranging from 0 for "no pain" to 10 for "worst pain imaginable." Patients are instructed to complete the pain

NRS in an electronic handheld diary by choosing the number that answers the following question regarding their bladder pain:

Please describe the average pain in your bladder over the last 24 hours.

The patient's baseline pain NRS will be the average of the 7-day "average pain in your bladder over the last 24 hours" NRS scores from the 7 reported days prior to randomization/1st IP insertion.

Study baseline for a patient is defined as the last measurement available prior to the first treatment.

Missing Data

Every effort will be made to obtain required data at each scheduled evaluation from all patients who have been enrolled. Missing data will only be imputed for the analysis of the primary efficacy variable.

7.2.1 Primary Efficacy Variables

The primary efficacy variable is the change in average daily bladder pain NRS at Week 4 Follow-up Visit post removal of 2nd IP of Treatment 1 as compared to study baseline.

The average daily pain NRS of the preceding 7 days (at least 5 consecutive days) will be calculated and used to calculate baseline and change from baseline at each scheduled visit. If no data are available for at least a period of 5 consecutive days, that average will be considered missing for that patient. The primary timepoint is 4-week follow up after removal of the 2nd IP of Treatment 1. If there is no valid Week 4 Follow-up NRS assessment and there is a valid Week 2 or 3 Follow-up NRS assessment, the Week 4 Follow-up value will be imputed using the latest of the 2 values that is available (ie, Week 2 or 3 Follow-up).

7.2.2 Secondary Efficacy Variables

There are 2 secondary efficacy variables:

• change from baseline in number of HLs assessed by the PI during cystoscopy

During each cystoscopy, the investigator will count the number of lesions visible while preforming the bladder scan for bladder mapping.

• change from baseline in composite score of HL calculated based on number, size, and possibly severity of the lesions

A standardized video capture protocol for bladder mapping will be followed in order to assess any changes in the number, the size and the severity, of lesions during the study as a result of treatment.

7.3 Hypothesis and Methods of Analysis

For the primary efficacy analysis, the null hypothesis is that the mean change from baseline in average daily bladder pain NRS at Week 4 Follow-up post IP removal visit is the same

between the LiRIS 400 mg/LiRIS 400 mg group and the LiRIS Placebo/LiRIS Placebo group (2 consecutive placebo's).

The alternative hypothesis is that the mean change from baseline in average daily bladder pain NRS at Week 4 Follow-up post IP removal is different between the LiRIS 400 mg/LiRIS 400 mg group and the LiRIS Placebo/LiRIS Placebo group.

Methods of Analysis

All continuous variables will be summarized showing the number, mean, median, standard deviation, minimum, and maximum values. Discrete variables will be summarized showing the frequency and percentage of the study population. As this is a phase 2 trial, there will be no p-value adjustment for multiplicity. Plots of efficacy variables (value and/or change from baseline) will be presented over time.

7.3.1 Demographics, Baseline Characteristics and Disposition Analyses

Demographic and baseline characteristic data, including age, race, ethnicity, and abnormal PE results will be summarized and presented by treatment group for Treatment 1 and Treatment 2 separately.

Patient disposition for both Treatment 1 and Treatment 2 will be displayed by treatment group. For those discontinuing the study prematurely, the reason for study termination will be recorded and time on study will be calculated.

7.3.2 Efficacy Analyses

All efficacy analyses will be performed on the mITT population. Analyses of the primary efficacy variable will also be performed on the PP population.

Plots of values and change from baseline or percentage in each variable category, as appropriate, will be presented by treatment over time.

All analyses are based on 2-sided tests with significance level of 0.10 unless otherwise specified.

7.3.2.1 Primary Efficacy Analyses

The primary endpoint was the change in bladder pain at Week 4 Follow-up Visit post last IP removal of Treatment 1 as compared to study baseline.

[figure not shown]
The average daily pain NRS of the preceding 7 days (at least 5 consecutive days) will be calculated and used to calculate change from baseline at each scheduled visit. Calculation of averages will employ available data without imputation. If no data are available for a given 7-day period (at least 5 consecutive days) that average will be considered missing for that patient.

[figure not shown]
The change from baseline in average daily bladder pain score at Week 4 Follow-up Visit post IP removal of Treatment 1 will be analyzed using the analysis of covariance (ANCOVA) model, using the baseline value as the covariate, and stratification factor (baseline bladder pain NRS: ≤ 5 or > 5) and treatment as factors. If there is no valid Week 4 Follow-up NRS assessment and there is a valid Week 2 or 3 Follow-up NRS assessment, the Week 4 Follow-up value will be imputed using the latest of the 2 values that is available (ie, Week 2 or 3 Follow-up).

The same ANCOVA analysis will also be performed at all other postbaseline timepoints.

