5.8.2 Qualification for Retreatment

Patients can request retreatment (Treatment 2) at any time from the Week 4 Follow-up clinic visit up through the Week 20 Follow-up clinic visit. A patient will be eligible to receive Treatment 2 (LiRIS 400 mg) only if all of the following criteria are met:

- completed Treatment 1 schedule of visits and procedures from the Week 4 Follow-up visit through qualification, in the opinion of the investigator
- negative urine dipstick reagent strip test (for leukocyte esterase and/or nitrites) and, in the investigator's opinion, patient is asymptomatic for a UTI on the day of study treatment
- negative urine pregnancy result (for patients that are child bearing potential) and are willing to continue using acceptable method of contraception
- Investigator continues to deem treatment is appropriate and no condition or situation exists which, in the investigator's opinion, puts the patient at significant risk from receiving treatment

6. **Response Measures and Summary of Data Collection Methods**

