7.7 Sample Size Calculation

Based on the assumption that 5% of the randomized patients will not be evaluable for the primary analysis, approximately 76 patients will be enrolled into the study to ensure 72 evaluable patients overall. At a randomization ratio of 2:1:1, 72 evaluable patients will ensure that there will be about 36 patients in the LiRIS 400 mg/LiRIS 400 mg group, 18 patients in the LiRIS Placebo/LiRIS 400 mg group, and 18 patients in the LiRIS Placebo group.

A sample size of 36 patients in the LiRIS 400 mg/LiRIS 400 mg group versus 18 patients in the LiRIS Placebo/LiRIS Placebo group will have 76% power to detect a difference of 1.152 in mean daily average bladder Pain NRS, assuming that the common standard deviation is 1.67 using a 1-sided 2-group t-test with a 0.05 significance level.

The standard deviation assumption is

based on the results of the TAR-100-105 open-label study, where the standard deviation is the Week 4 Follow-up raw average daily NRS.

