11.1.1 Other Analysis of Primary Efficacy Variable

The ANCOVA Analyses of the primary efficacy variable will also be performed using the PP population and with no imputations for missing Week 4 Follow-Up weekly mean of the average daily bladder pain NRS.

Average daily 24-hour pain NRS and the corresponding change from baseline values will also be summarized for each week post randomization for the Treatment 1 Period (see Table 17.2.1–1). For each weekly (mean) change from baseline values, the ANCOVA analysis outlined for the primary timepoint will be applied without any imputation for missing values.

A sensitivity analysis using a mixed-effects model for repeated measures (MMRM) (Mallinckrodt et al, 2001a and 2001b) based on all post-baseline weekly mean data up to Treatment 1 Week 4 Follow-Up, will be performed to compare treatment effect at each post-baseline week (see Table 17.2.1–1). The MMRM analysis will include treatment group, assessment week, and treatment group–by-assessment week interaction as factors and baseline value as covariate. An unstructured covariance matrix will be used to model the correlation over time in change from baseline values for the primary efficacy variable.

Plots of weekly mean of the average daily bladder pain values and the associated change from baseline values will be presented by treatment group over time.

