The data derivations and definitions listed in this section are to be applied to all analyses described in this analysis plan, unless otherwise stated.

- In this study there are two treatment periods:
 - Treatment period 1: for patients that just receive treatment in the randomized and blinded phase of the trial, it covers the period from the first Treatment 1 IP insertion to study exit. In contrast, for patients that receive IP insertions in both the randomized phase of the study (Treatment 1) and the open label phase of the study (Treatment 2) it covers the period from first Treatment 1 IP insertion up to Treatment 2 IP insertion,
 - Treatment period 2: covers the period from Treatment 2 IP insertion to study exit.
- Study days for each treatment period X (X=1 or 2) will be calculated as:
 - Study day of Treatment X = visit date (day 1 of Treatment X) + 1.
- The baseline value of an assessment will be the last value recorded prior to the patient being inserted with first Treatment 1 IP on Day 1.
- Unless otherwise stated no imputation will be performed for missing data. All analyses will be based on the observed data.
- For analyses that are by stratification factor, actual stratification levels rather than randomization stratification levels will be used.
- Data will be pooled across the investigational sites.
- Descriptive statistics for continuous/ordinal data include the sample size (N), mean, standard deviation (SD), median, minimum (Min), and maximum (Max) and 95% confidence intervals.
- Summary statistics for categorical variables include sample size (N), frequency count (n), and percentage (%).

17.2.1 **Pain Data Derivations**

A pain assessment tool will be utilized in the study to capture the average daily pain and the daily worst pain scores on an electronic hand held device. Patients will be asked to rate their daily pain on a pain NRS consisting of an 11 point integer scale ranging from 0 for "no pain" to 10 for "worst pain imaginable". The pain assessment will continue every day up to and including the day prior to the Exit visit.

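### After Week 4 Follow-up the weekly ANCOVA compares only patients who have not yet taken open-label LiRIS; if requests follow pain, later differences are likely biased toward zero

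*Protocol*

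**What the plan says.** **Retreatment.** Protocol 5.8.2: "Patients can request retreatment (Treatment 2) at any time from the Week 4 Follow-up clinic visit", up to the Week 20 Follow-up visit. Protocol 5.6.2 gives LiRIS 400 mg to every arm, and SAP 5.0 calls this treatment open label. The retreatment criteria that can be read contain no pain threshold.

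**End of Treatment 1 data.** For a retreated patient, SAP 17.2 defines Treatment period 1 this way: "it covers the period from first Treatment 1 IP insertion up to Treatment 2 IP insertion".

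**Later-week comparison.** Protocol 7.3.2.1: "The same ANCOVA analysis will also be performed at all other postbaseline timepoints". SAP 11.1.1 does this for each weekly mean change in the Treatment 1 Period: "the ANCOVA analysis outlined for the primary timepoint will be applied without any imputation for missing values".

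**Repeated-measures model.** SAP 11.1.1 plans an MMRM as a sensitivity analysis, but only "based on all post-baseline weekly mean data up to Treatment 1 Week 4 Follow-Up".

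**Other durability summary.** SAP 10.1 displays Treatment 1 duration by group, counted to Treatment 2 insertion or exit, and suggests reading it as duration of effect.

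**The concern.** Until Week 4 Follow-up, patients are missing for ordinary reasons, and the plan allows 5% for this. From then on there is a second reason, chosen by the patient after randomisation: she can leave the comparison to receive the active product. An observed-case ANCOVA at Week 12 or Week 20 compares those who stayed on LiRIS with those who stayed on placebo.

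Suppose patients with more pain are more likely to ask, and both blinded arms behave alike. Placebo then loses more of its worst patients than active does, the remaining groups look more similar, and a benefit that lasts can appear to fade. Sixteen of the 20 follow-up weeks are exposed to this. The planned model that could use each patient's earlier pain values does not reach those weeks. The trial is meant to inform further development, so a false impression of fading would matter.

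**Working it through.** **1. The plan's own figure.** Protocol 7.7 claims "76% power to detect a difference of 1.152 in mean daily average bladder Pain NRS" for 36 versus 18 patients, SD 1.67, with a "1-sided 2-group t-test with a 0.05 significance level".
- Standard error: 1.67 × √(1/36 + 1/18) = 0.482. Noncentrality: 1.152 / 0.482 = 2.39.
- Noncentral t with 52 df gives 76.2%; the normal approximation gives 77.2%. The stated 76% is reproduced.
- Protocol 7.3.2 adds: "All analyses are based on 2-sided tests with significance level of 0.10 unless otherwise specified". A two-sided 0.10 test has the same critical value as a one-sided 0.05 test.
- Enrolment: 72 / 0.95 = 75.8, so 76.

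These figures concern Week 4 only. The plan gives no retreatment rate and no within-patient correlation, so everything below rests on assumptions.

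**2. Simulation at trial size.** From the plan: 36 versus 18 patients, a true benefit of 1.152 (here held constant at every visit), SD 1.67. Assumed: visits at Weeks 4, 8, 12, 16 and 20; within-patient correlation ρ; and leaving after each visit with logit(p) = b0 + b1 × (pain change − midpoint of the two arm means), the same in both arms. Positive values favour LiRIS.

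Central case (b0 = −1.4, b1 = 1.0, ρ = 0.7):

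| Week | Observed-case estimate | Same, 100 times the patients | Active remaining | Placebo remaining | Chance of significance |
|---|---|---|---|---|---|
| 4 | 1.19 | 1.16 | 100% | 100% | 77% |
| 8 | 0.96 | 0.96 | 80% | 63% | 49% |
| 12 | 0.86 | 0.85 | 66% | 45% | 36% |
| 16 | 0.76 | 0.77 | 57% | 34% | 27% |
| 20 | 0.71 | 0.72 | 50% | 27% | 21% |

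The 1.19 at Week 4 is simulation error. At Week 20 about 0.50 × 36 = 18 active and 0.27 × 18 ≈ 5 placebo patients remain.

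Varying b0 from −2.2 to −0.8, b1 between 0.5 and 1.0, and ρ from 0.5 to 0.9 gives Week 20 estimates of 0.64 to 0.98. The shortfalls are 1 − 0.98/1.152 = 15% and 1 − 0.64/1.152 = 44%.

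**3. Weekly requests instead.** Assumed: logit(p) = a + b × (previous week's pain − 4.8), with (a, b) = (−4, 0.5), (−3.5, 0.7) and (−3, 1.0).
- With AR(1) correlation 0.7 alone, Week 20 estimates are 1.13, 1.08 and 0.95, with 32%, 53% and 75% of placebo and 20%, 31% and 46% of active retreated.
- Other within-patient correlation structures widen the range to 0.78 to 1.14. The smallest shortfall is 1 − 1.14/1.152 = 1%.

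**4. Other request patterns (Week 20).**
- Unrelated to pain: 1.15. No bias, but power is 40%.
- Good responders ask, same rule in both arms: 0.93, also toward zero.
- Pain-driven in active, random in placebo: 1.96, away from zero.

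**5. Using the pain history.** A missing-at-random estimate from values before retreatment was run under the step 2 model, here with a simple difference in means as the observed-case comparator. Simulated trials with fewer than three patients left in either arm were dropped.
- Light leaving (b0 = −2.2, b1 = 0.5): 1.15, against 0.99 for observed cases.
- Central case: 1.13, against 0.72.
- Heavy leaving (b0 = −0.8, b1 = 1.0): 1.00, against 0.65.

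**6. Feasibility of the MMRM.** Weekly data over 4 treatment and 20 follow-up weeks give 24 timepoints, so an unstructured matrix has 24 × 25 / 2 = 300 parameters for 76 patients. Five timepoints need 5 × 6 / 2 = 15. Under the step 3 request rules, a five-timepoint MMRM at 36 versus 18 ran in every simulated trial. Its average Week 20 estimate was 1.01 to 1.15, against 0.77 to 1.12 for observed cases, and it was never the more biased of the two.

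**The case against.** **Direction.** A reader might infer that the later estimates are certainly biased toward zero. The documents do not support that: no visible criterion ties a request to pain, random requests give no bias, and a rule that differs by arm can reverse the sign. This stands, so the direction is conditional. A common, pain-related rule remains the natural expectation, because Treatment 1 is blinded, Treatment 2 is another dose for a painful condition, and SAP 10.1 itself links time to retreatment with effect.

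**Other evidence.** A reader might infer that these weeks are the only evidence on how long benefit lasts. They are not. Treatment 1 duration by group counts early retreatment instead of discarding it. Weekly summaries include N, and disposition is shown for both treatments, so much of the count information will exist. None of this corrects the weekly treatment differences.

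**Size.** The percentages come from assumed request rules and correlations, and they move a great deal with them. This stands.

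**The remedy.** It rests on missing-at-random and targets a hypothetical quantity, the difference without retreatment. Missing-at-random did well in the simulations partly because leaving was generated from observed pain. The covariance also matters: with AR(1) data, compound symmetry gave 1.19, 1.24 and 1.27, or 3% to 10% too large. These points shape the fix but do not remove the need for it.

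**Importance and visibility.** These are supportive analyses in a phase 2 trial with no multiplicity adjustment. Table 17.2.1-1 and parts of the efficacy sections are not shown, so handling set out there cannot be excluded.

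**Conclusion.** The structural point holds. After Week 4 Follow-up the plan's between-arm tests use only patients not yet retreated, without imputation, and the MMRM does not cover those weeks. If requests follow pain by one rule in both arms, the later differences are likely biased toward zero, by about 1% to 44% at Week 20 in the simulations. That range is illustrative: it depends on assumed retreatment rates, request rules and correlations, none of which the plan supplies. Whatever the direction, the later-week estimates cannot be read as randomised comparisons without a further assumption, and the plan as shown states none.

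A reader might also infer that the trial's main result is compromised. It is not: retreatment opens only at the Week 4 Follow-up visit, so the primary comparison is unaffected. The change is worth making, but it concerns supportive results only.

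**What to change.** In SAP 11.1.1:
- Add an MMRM over follow-up Weeks 4, 8, 12, 16 and 20, using all Treatment 1 values at those weeks up to Treatment 2 insertion, with an unstructured covariance. Name the fallback in advance; Toeplitz is one candidate, since it contains both compound symmetry and AR(1).
- State that it estimates the difference had patients not been retreated, under missing-at-random.
- Use it as the supportive comparison after Week 4.
- Label the weekly observed-case ANCOVA after Week 4 as descriptive, and show the number still in Treatment 1 by arm beside each estimate and plot.

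Cost: SAP wording and one more run of a planned type of model, on diary data already collected. The result relies on missing-at-random. Some bias may remain if retreatment is heavy (1.00 against a true 1.152 in the heaviest case in step 5), or if pain between the modelled weeks drives requests.
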